9.4 Analyses Plans

Analyses of primary and secondary endpoints as well as exploratory analyses will be conducted by [REDACTED] the designated biostatistician for this protocol. Demographic and other baseline characteristics will be summarized in the aggregate manner. For continuous demographic/baseline variables including age, weight, and vital signs, results will be summarized and presented as N, mean, standard deviation, median, and minimum and maximum values. For categorical variables such as race/ethnicity, the number and percentage of subjects will be used. Statistical comparisons of these baseline characteristics will be performed using the Wilcoxon rank-sum test for continuous variables and Fisher's exact test for categorical variables.

9.4.1 Analysis Population

The safety population will include all enrolled patients who receive at least one dose of the study drug. All patients will be evaluable for toxicity and safety assessment from the time of their first treatment with the study drug.

The evaluable population for efficacy will include all enrolled patients who have received at least one dose of study drug (unless determined to be ineligible and replaced for reasons such as inability to comply or withdrawal of consent). These patients will have their response classified according to the definitions stated below.

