2.4 Endpoints

2.4.1 Primary Endpoint

- Median TTP will be calculated in months from date of first dose of protocol therapy to date of removal from study for progression. For patients removed from study for other reasons than progression (such as toxicity, withdrawal of consent, death without documented progression, or other reasons without clinical or radiographic evidence of tumor progression), TTP will be censored at the date last known to be progression-free.

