3.2 Number of Subjects

The target sample size is 25 evaluable patients for the primary endpoint. With the expectation of approximately 10% ineligibility rate, the expected maximum enrollment will be 28 patients. Eligible patients who receive at least one dose of protocol therapy will not be replaced. Patients will be replaced and removed from study if determined to be ineligible after enrollment (for reasons such as inability to comply/withdrawal of consent or other ineligibility)

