7.1.2 Time to Event Endpoints

Time to Progression (TTP)

TTP is defined as the duration from date of first dose of protocol therapy to date of removal from study for radiographic (per RECIST 1.1) and/or clinical progression including death attributed to progression. For patients removed from study for other reasons than progression (such as toxicity, withdrawal of consent, death without documented progression, or other reasons without clinical or radiographic evidence of tumor progression), TTP will be censored at the date of study discontinuation.

Time to Treatment Failure (TTF)

TTF will be measured from date of first dose of protocol therapy to date of study discontinuation for progression, death, or toxicity. For patients removed from study for other reasons (such as noncompliance or withdrawal of consent), TTF will be censored at the date of study discontinuation.

Progression-Free Survival

Progression-free survival (PFS) is defined as the duration of time from date of first dose of protocol therapy to time of documented radiographic and/or clinical disease progression or death from any cause. Patients who have not progressed or died are censored at the date last known to be progression-free.

Overall Survival (OS)

Median OS for all enrolled patients who receive at least one dose of protocol therapy will be calculated from date of first dose of protocol therapy until date of death, using chart review and/or follow up phone calls to determine date of death in patients after removal from study. The survival of patients still alive after 5 years of follow up post study discontinuation will be censored. Alive patients are censored at the date last known alive.

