9.1.2 Primary Endpoint

Median TTP will be calculated in months from date of first dose of protocol therapy to date of removal from study for radiographic (per RECIST 1.1) and/or clinical progression including death attributed to progression. For patients removed from study for other reasons than progression (such as toxicity, withdrawal of consent, or death from other causes than documented radiographic and/or clinical progression), TTP will be censored at the date last known to be progression-free.

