9.2 Determination of Sample Size and Accrual Rate

9.2.1 Sample Size and Power Estimate

The sample size for this phase II study will be 25 patients under the assumption that the time to progression is approximately exponentially distributed and patients come onto study uniformly

during the study accrual. A sample size of 25 evaluable patients will have sufficient power to detect the difference between the null hypothesis that the median TTP is less than 3 months (based on historical controls) and the alternative hypothesis that the median TTP is more than 6 months. The study will have a 1-sided significance level of 10% and a power of 88% under the exact test for comparison of the TTP rates between $p_0 < 25\%$ versus $p_1 > 50\%$ at 6 months.

A median TTP of > 6 months would constitute a meaningful outcome in advanced HCC, based upon the benchmarks of first-line TTP of 5.5 months in the SHARP study and 2.8 months in the Asia-Pacific study.(Llovet, Ricci et al. 2008; Cheng, Kang et al. 2009) If median TTP is > 6 months in this study, a randomized phase II trial to compare the combination therapy to single-agent sorafenib should be considered. Such a trial would be much larger and more costly, however, and should not be undertaken prior to the current study to confirm that there is tolerability and a signal of efficacy to warrant proceeding with the larger trial, noting in particular the challenges to accrual in first-line HCC studies historically, as faced by contemporary cooperative group studies CALGB 80802 and ECOG 1208.

Accrual of 25 paired archival tumor and blood specimens also constitutes a meaningful endpoint in that it will enable future biomarker studies in subsets of patients with radiographic response, AFP response, prolonged stable disease, and primary progression, including potential exploratory studies for association with tissue biomarkers of mTOR pathway activation (such as pS6 staining).(Villanueva, Chiang et al. 2008)

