9.4.2 Analysis of Primary Endpoints

Kaplan-Meier methods will be used to summarize the primary endpoint (median TTP) with 95% confidence intervals. The proportion of patients with TTP equal to or exceeding 6 months will also be calculated and reported along with 95% confidence intervals.

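### A dosed patient who withdraws consent or cannot comply may be either censored or removed and replaced, and Section 3.2 does not say which rule governs

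*Combined protocol and SAP*

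**What the plan says.** Three parts of the combined protocol and SAP bear on the same patients.

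- **Analysis population.** Section 9.4.1 starts from all enrolled patients with at least one dose of study drug, then makes an exception: "unless determined to be ineligible and replaced for reasons such as inability to comply or withdrawal of consent". Section 7.1.1.1 has the same exception in its definition of evaluable for efficacy.
- **Replacement.** Section 3.2 states "Eligible patients who receive at least one dose of protocol therapy will not be replaced". Its next sentence removes and replaces patients "determined to be ineligible after enrollment (for reasons such as inability to comply/withdrawal of consent or other ineligibility").
- **Endpoints.** Section 2.4.1 censors TTP for patients who leave for reasons "such as toxicity, withdrawal of consent, death without documented progression". Section 9.1.2 does the same for reasons "such as toxicity, withdrawal of consent, or death from other causes than documented radiographic and/or clinical progression", and the TTP definition in 7.1.2 also names withdrawal of consent. For TTF, Section 7.1.2 covers patients who leave for reasons "such as noncompliance or withdrawal of consent), TTF will be censored at the date of study discontinuation", and 9.1.3 agrees.

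Section 3.4 lists patient withdrawal and inability to comply with study procedures among the ordinary reasons to stop treatment. Overall survival (2.4.2, 7.1.2, 9.1.3) covers all enrolled dosed patients, with no such exception.

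**The concern.** A patient who takes study drug and later withdraws consent fits both rules. The endpoint sections keep and censor that patient; the population sections allow the same patient to be declared ineligible, removed and replaced. Eligibility is meant to separate the two cases, but Section 3.2 uses the two disputed events as its examples of ineligibility, so it does not decide between them.

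Inability to comply can be a genuine baseline failure, because inclusion criterion 17 and exclusion criterion 21 concern willingness and ability to comply. Withdrawal of consent after dosing is a later event and cannot be a failed entry criterion. The text does not confine removal to failures present before dosing and sets no time limit.

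The trial is open-label with one arm, so the classification can be made once a patient's course is known. The response-rate denominator, the 6-month TTP proportion and the Kaplan-Meier median could all depend on it, and the TTP and OS populations could differ.

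**Working it through.** **Inputs from the documents.** 25 evaluable patients, about 10% ineligibility and a maximum of 28 enrolled (3.2); 6-month TTP rates of 25% and 50%, corresponding to exponential medians of 3 and 6 months (9.2.1); and "The study will have a 1-sided significance level of 10% and a power of 88% under the exact test" (9.2.1).

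**Assumptions.** The documents do not give the number, outcomes or timing of affected patients. I take 1 to 3 removals. Three is a ceiling, because 3.2 attributes the 28 − 25 = 3 extra places to ineligibility.

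**1. Reproduce the design.** X is the number of 25 patients reaching 6 months without progression, binomial. The plan prints no cutoff.
- P(X ≥ 9 | 25, 0.25) = 0.149, above 0.10.
- P(X ≥ 10 | 25, 0.25) = 0.071, and P(X ≥ 10 | 25, 0.50) = 0.885, matching the stated 88%.

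The inferred cutoff is therefore 10 of 25.

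**2. Upper bound for type I error.** If k removed patients are all non-successes, 25 + k patients are dosed and 10 successes among them are enough. The error is P(X ≥ 10 | 25 + k, 0.25). If exactly one removed patient would have succeeded, 11 are needed.

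| Removed | All non-successes | One would have succeeded | Unrelated to outcome |
|---|---|---|---|
| 1 | 0.091 | 0.040 | 0.071 |
| 2 | 0.113 | 0.053 | 0.071 |
| 3 | 0.138 | 0.068 | 0.071 |

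Two removals exceed 0.10, but only in the first column.

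**3. Independent withdrawal, dropped or censored.** TTP is exponential with hazard λ. Withdrawal is exponential with hazard λ × 3/25, so the chance of withdrawing before progression is 3/28. Dropped patients are replaced until 25 remain. Mean Kaplan-Meier medians by simulation:

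| Handling | True median 3 | True median 6 |
|---|---|---|
| Kept and censored | 3.14 | 6.25 |
| Dropped, any time | 2.76 | 5.51 |
| Dropped, before 6 months only | 2.86 | 5.99 |
| Dropped, first 2 months only | 3.05 | 6.24 |

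With no withdrawal the means are 3.10 and 6.17, so the censored figures carry only small-sample bias.

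A direct check agrees. Dropping withdrawals at any time leaves times with hazard λ × 28/25. At true median 6 the remaining 6-month rate is 0.5^1.12 = 0.460, and P(X ≥ 10 | 25, 0.460) = 0.79. At true median 3 the rate is 0.25^1.12 = 0.212, and the rejection probability is 0.025.

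Timing matters because, at true median 6, the share of withdrawals that occur after 6 months is also 0.5^1.12 = 0.46; those patients have already succeeded. Dropping only withdrawals before 6 months gives a rate of 0.460 / (1 − 3/28 × 0.540) = 0.488 and power of about 0.86. The corresponding type I error is 0.044.

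**4. Response rate.** With an illustrative 3 responders, 3/25 = 12.0% and 3/28 = 10.7%.

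**The case against.** The strongest defence is that the documents do contain a separator. Eligible dosed patients are not replaced, and 7.1.1.1 and 9.4.1 require a patient to be both found ineligible and replaced, so withdrawal alone should not suffice. Compliance is an entry criterion, so that example can be read as a baseline failure. This stands for inability to comply. It fails for withdrawal of consent, and reading the exception as pre-dose withdrawal only fails because both sections apply it to patients already dosed.

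A second defence is that the error rates concern a test that the primary analysis section does not schedule. Section 9.4.2 plans a Kaplan-Meier median with a confidence interval, and "The proportion of patients with TTP equal to or exceeding 6 months will also be calculated" without saying how. That is fair: the cutoff is inferred from 9.2.1, and the figures show sensitivity, not a stated operating characteristic.

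Third, the worst case needs removal that perfectly selects future failures. Patients removed for progression are TTP events under 7.1.2 and 9.1.2, and progression is nowhere listed as grounds for replacement. This also stands; the figures are an upper bound only.

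A reader might infer that the median is safe from inflation. That holds only if removed patients were still progression-free. If patients who had already progressed were dropped, the median could rise.

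**Conclusion.** The conflict is real and should be resolved. A written exclusion can take dosed patients out of the efficacy population for events that the endpoint definitions keep and censor, and nothing in the plan settles which applies.

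No single direction of bias follows. Across the scenarios above, type I error at the inferred cutoff runs from 0.025 to 0.138, with no inflation if removal is unrelated to outcome. The fall in the mean Kaplan-Meier median at a true 6 months runs from 6.25 − 5.51 = 0.74 months (any-time dropping) to 0.01 (first 2 months only). Any-time dropping is the less plausible case, since it calls patients ineligible after they have passed 6 months. The response rate moves by 1.3 points in the example.

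The stronger reading, that the plan's 10% level or 88% power is wrong or that its TTP result will be inflated, is not supported. The stated power reproduces, and the documents give neither the number nor the outcomes of affected patients. The defect is that the rule can be chosen after outcomes are seen, in a trial of 25 whose median TTP informs whether a randomized trial follows (1.3, 9.2.1).

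**What to change.** In 3.2, 7.1.1.1 and 9.4.1, use one definition:

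- The efficacy population is all patients with at least one dose, apart from the pre-dose eligibility failures below.
- Exclude and replace only patients who were never dosed, or who are shown from pre-dose records to have failed an entry criterion, judged without knowledge of outcome.
- Keep post-dose withdrawal and noncompliance in the analysis: censored for TTP as in 9.1.2, counted in the response-rate denominator, and not replaced.

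The cost is wording in three sections and a possibly slightly lower response rate or 6-month proportion.

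A sensitivity analysis counting withdrawals before 6 months as not reaching 6 months is optional. On that basis, if 1, 2 or 3 of the 25 withdraw, power at a true 50% is P(X ≥ 10) with 24, 23 or 22 patients: 0.846, 0.798 or 0.738, against 0.885.

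Separately, and of minor consequence, Section 5.3 makes a patient evaluable for safety after a dose of both drugs, whereas 7.2, 9.4.1 and 9.5 require one dose of study drug. These should be reconciled.

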9.4.2 Analysis of Primary Endpoints

Kaplan-Meier methods will be used to summarize the primary endpoint (median TTP) with 95% confidence intervals. The proportion of patients with TTP equal to or exceeding 6 months will also be calculated and reported along with 95% confidence intervals.

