9.4.4 Exploratory Analyses/Assessments

- CTC levels: Baseline level of CTC (detectable or undetectable) will be compared to proportion with TTP at 6 months to determine if there is an association using Fisher's Exact tests. Change in CTC levels (increase or decrease) after 1 and 2 cycles will be compared to proportion with TTP at 6 months to determine if there is an association using Fisher's Exact tests. Markers of mTOR pathway activation: Descriptive statistics will summarize the IHC parameters of staining intensity, percentage positivity, distribution, and intracellular localization for each protein. Due to possible limited specimen quantity, IHC outcomes will be dichotomized. Activation will be measured by % positive cells and intensity using published IHC cutpoints for high/low: cytoplasmic pAkt > 40% or 2-3+, cytoplasmic PTEN intensity < 10% or 0-1+, cytoplasmic pS6RP > 70% or 2-3+, or LKB1 0-1.⁷⁻¹² Univariate analysis using Cox's model will be performed to test whether the dichotomized expression of each protein using the published cutpoints is a significant predictor of TTP. Results for each test will include the hazard ratio (HR) with 95% confidence intervals. The association between each protein and the two binary coding schemes for AFP decline ($\geq 50\%$ or $\geq 20\%$) on C2D1 will be tested using Fisher's exact test. Results for each test will be summarized with proportions with pathway activation and 95% confidence intervals for each AFP subset. Each patient will also be categorized as having overall mTOR pathway activation (defined as any combination of high pAKT, high pS6RP, low PTEN, and/or low LKB1) or not. This binary variable will also be examined for its relationship with TTP, OS, AFP response, and other clinical endpoints using the same methods described above. For each test of association with AFP change, based upon Fisher's exact test large differences can be detected (e.g. 10% among 7 patients with marker-low, 80% among 8 patients with marker-low) (power=81%, $\alpha_2=10\%$). The sample size is too small to test for a difference in TTP, OS, or other clinical endpoints according to pathway activation status. The expected sample size will be ≥ 25 cases (expect 40 to 45 cases) with IHC-quality archival tumor, with the expectation that $\sim 75\%$ of cases will be evaluable for TTP ($n \geq 18$) and 60% evaluable for AFP response on C2D1 ($n \geq 15$).

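### The 88% power assumes that all 25 patients have a known 6-month TTP status, and the plan has no rule for patients censored before 6 months

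*Combined protocol and SAP*

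**What the plan says.** Section 9.2.1 sets the design. "A sample size of 25 evaluable patients will have sufficient power to detect the difference between the null hypothesis" of a median TTP below 3 months and the alternative of a median above 6 months, with TTP taken as approximately exponential. It continues: "The study will have a 1-sided significance level of 10% and a power of 88% under the exact test" of 6-month TTP rates, 25% against 50%.

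Section 2.4.1 deals with patients who leave for reasons other than progression, such as toxicity, withdrawal of consent or death without documented progression: "TTP will be censored at the date last known to be progression-free". Section 9.1.2 has the same rule. Section 5.2 adds that stopping either drug removes the patient from study.

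Section 3.2 raises enrolment from 25 to 28 for an expected ineligibility of about 10%. It says that eligible dosed patients are not replaced. The same section, and 9.4.1, nevertheless list withdrawal of consent and inability to comply among reasons for replacement. No allowance is made for censoring.

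Section 9.4.2 uses Kaplan-Meier for the median TTP with a 95% confidence interval, and then adds: "The proportion of patients with TTP equal to or exceeding 6 months will also be calculated and reported along with 95% confidence intervals". Section 9.4.3 repeats the 6-month proportion for TTP, PFS and TTF. Neither section restates the exact test, gives its cutoff, or says how a patient censored before 6 months is treated.

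**The concern.** An exact binomial test needs a yes or no for each patient at 6 months. A patient who stops for toxicity at month 3 without progression has neither. There are three ways to proceed: count the patient as a failure, leave the patient out, or use a Kaplan-Meier estimate. They have different power and type I error, and the plan does not choose. In a 25-patient trial with a cutoff of 10, one or two patients can reverse the result, and the choice could be made after the data are seen.

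The literal wording points to the least favourable option. The recorded TTP of a patient censored at month 3 is below 6 months, so that patient drops out of the numerator. The efficacy population of 9.4.1 (at least one dose) keeps the patient in the denominator.

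**Working it through.** **Inputs.** n = 25, one-sided 10% level, rates 25% and 50%, exponential TTP with medians of 3 and 6 months (9.2.1). Under that model S(6) = 2^(-6/3) = 0.25 and 2^(-6/6) = 0.50, which agrees with the stated rates. Section 3.7.2 gives every patient the potential for at least 6 months of follow-up, so administrative censoring before 6 months is not the issue. The early-censoring rates below are assumptions.

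**1. The plan's figure.** For X ~ Bin(25, p):
- P(X ≥ 9 | 0.25) = 0.149, above 0.10
- P(X ≥ 10 | 0.25) = 0.0713, so the cutoff is 10
- P(X ≥ 10 | 0.50) = 0.8852

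The stated 88% is reproduced, with all 25 outcomes known.

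**2. Early-censored patients counted as failures.** If a fraction d of would-be successes is lost, the success probability becomes 0.50(1 − d):
- d = 10%: P(X ≥ 10 | 0.45) = 75.8%; type I error P(X ≥ 10 | 0.225) = 3.8%
- d = 20%: P(X ≥ 10 | 0.40) = 57.5%; type I error P(X ≥ 10 | 0.20) = 1.7%

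Now let a share of *all* patients be censored before 6 months, with a constant removal hazard c independent of progression. With λ = ln 2 / 6 = 0.1155, the share censored is c/(c + λ) × [1 − exp(−6(c + λ))], and the success probability is 0.50 × exp(−6c).

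| Share censored (under the alternative) | c per month | exp(−6c) | Success prob. | Power | Type I error at the same c |
|---|---|---|---|---|---|
| 10% | 0.0246 | 0.863 | 0.431 | 69.5% | 2.9% |
| 20% | 0.0530 | 0.728 | 0.364 | 42.6% | 0.9% |

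These hazards would remove 13.7% and 27.2% of patients by 6 months if nobody progressed. The share actually censored is lower because some patients progress first.

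**3. Early-censored patients excluded, cutoff reset.** If the known patients still succeed at 50%:

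| Known patients | Cutoff | Type I error | Power |
|---|---|---|---|
| 24 | 10 | 5.5% | 84.6% |
| 23 | 9 | 9.6% | 89.5% |
| 22 | 9 | 7.5% | 85.7% |
| 21 | 9 | 5.6% | 80.8% |
| 20 | 9 | 4.1% | 74.8% |

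So power is about 75% to 90%, and it does not fall steadily. Under exponential removal the rate among known patients is itself below 50%, because early progressors stay in while would-be successes leave. Simulated power is then 82% with 8% censored and 68% with 19% censored.

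**4. Kaplan-Meier estimate at 6 months.** Reject if the one-sided 90% lower log-log bound exceeds 25%. With no early censoring this is the same rule as 10 of 25. The statistic is [ln(−ln 0.25) − ln(−ln S)] / se, with se = √((1 − S)/(25S)) / |ln S|:
- S = 10/25: (0.327 + 0.087)/0.267 = 1.55, above 1.28, reject
- S = 9/25: (0.327 − 0.021)/0.261 = 1.17, below 1.28, do not reject

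Simulation (40,000 trials, exponential TTP, independent exponential censoring) gives power of about 88% at 10% censored and 85% at 20%, with type I error of about 9%.

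**The case against.** The main objection is that nothing in the plan says censored patients are failures. A reader might infer that it does, because the literal proportion works that way, but the documents are silent. In 9.4.3 the 6-month proportions directly follow the sentence on Kaplan-Meier methods, and exact binomial intervals are named only for response rates. A Kaplan-Meier landmark is therefore a fair reading of the proportion. If it is the intended one, the bias disappears. This stands, and it limits the point to an unstated rule.

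A reader might also infer that an active regimen would be dropped on the strength of this proportion. Sections 1.3 and 9.2.1 tie the step to a randomized trial to the median TTP, which 9.4.2 estimates by Kaplan-Meier. The 6-month proportion is an additional estimate, so that consequence is not established. The stated power, however, belongs to the 6-month test and not to the median.

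Section 9.4.4 expects about 75% "of cases will be evaluable for TTP". It is tempting to read this as the expected evaluability of the trial. It concerns an archival-tissue set pooled with another study and gives no early-censoring rate for the primary cohort.

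Nor is the 88% lost under every handling as soon as one patient leaves: 23 known patients with a reset cutoff give 89.5%. Replacement for withdrawal or non-compliance (3.2, 9.4.1) may soften the loss, though 3.2 also says eligible dosed patients are not replaced. No replacement is offered for toxicity removals or for deaths without progression.

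Finally, counting failures is conservative on type I error. That is correct, and it would be a legitimate rule if prespecified with its power.

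**Conclusion.** The point holds as a gap in specification. The 88% is correct for 25 known outcomes. The protocol itself produces patients without one, and no section says how the exact test or the 6-month proportion treats them. On the literal reading the rate is biased downward, and power is about 70% or 43% when 10% or 20% of all patients are censored early. Exclusion gives about 75% to 90% for 20 to 24 known patients if their success rate stays at 50%. A Kaplan-Meier test keeps about 85% to 88%.

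These figures rest on assumed censoring rates, exponential TTP and censoring independent of progression. Independence is open to question for toxicity and death. The gap should be fixed before analysis, but it does not undermine the Kaplan-Meier median.

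**What to change.** - **Sections 9.4.2 and 9.4.3:** define the 6-month TTP, PFS and TTF rates as Kaplan-Meier estimates at 6 months, with confidence intervals to match.
- **Decision rule:** state that the 25% null is rejected if the one-sided 90% lower log-log Kaplan-Meier bound for the 6-month TTP rate exceeds 25%. This keeps the 10% level of 9.2.1 and equals the 10-of-25 rule when nobody is censored early.
- **Section 9.2.1:** say that the 88% assumes no censoring before 6 months. Restate power at assumed rates: about 88% at 10% and 85% at 20%, with type I error of about 9%, given censoring independent of progression.

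The cost is wording only, with no added patients or procedures. The stated power becomes slightly less favourable at the higher censoring rate.
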